10.1.1 Confinement, Return Visits, and Follow-Up

Patients will be admitted to the CRU on Day -8, at the time indicated by the CRU, until after completion of study procedures on Day 3 as indicated in the Study Events Flow Chart ([Section 6](#)). At all times, a patient may be required to remain at the CRU for longer at the discretion of the PI or designee.

All patients who receive the study drug or matching placebo (including patients who terminate the study early) will return to the CRU on Day 14 (\pm 2 days) for coagulation tests, immunogenicity sample collection, and to determine if any AE has occurred since the last study visit.

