13.8 Blood Volume for Study Assessments

Table 3. Blood Volume during the Study

Sample Type	Number of Time Points	Approximate Volume per Time Point * (mL)	Approximate Sample Volume Over Course of Study (mL)
Screening laboratory safety tests (including hematology, serum chemistry, serology, and coagulation), FSH (for postmenopausal female patients only) and serum pregnancy (for female patients only).	1	16	16
On-study hematology and serum chemistry (this includes serum pregnancy for female patients only when scheduled at the same time)	2	12.5	25
On-study coagulation (aPTT, PT/INR, fibrinogen, and TT)	12	3.5	42
On-study platelet count only **	Up to 10	3.5	Up to 35
On-study BUN only **	Up to 10	3.5	Up to 35
Blood for PD (APC-PCI) (ships to Celerion)	8	4	32
Blood for protein C (ships to Aronora)	16	2	32
Blood for plasma immunogenicity (E-WE thrombin plasma ADA) (ships to Haemtech Biopharma)	2	4.5	9
Blood for serum immunogenicity (WT thrombin serum ADA) (ships to Haemtech Biopharma)	2	5	10
Total Blood Volume (mL)→			Up to 236***

* Represents the largest collection tube that may be used for this (a smaller tube may be used).

** Platelet count and BUN values will be taken from the hematology, serum chemistry samples when these are scheduled to be collected at the same time. Samples will not be taken twice at the same timepoint.

*** If additional safety or PD analysis is necessary to obtain sufficient plasma/serum for analysis, additional blood may be obtained (up to a maximum of 50 mL).

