14.3.1 Safety and Tolerability Analyses

All safety data will be populated in the individual CRFs. All safety data will be listed by patients.

The placebo patients from all cohorts will be pooled into a single placebo group for all summaries and presentations.

Dosing dates and times will be listed by patient.

Incidence and time of bleeding from the HD access sites on the AV fistula (or AV graft), as described in [Section 13.2.6](#), will be counted and recorded. Active treatment versus pre-treatment, placebo, and post-treatment results will be compared.

AEs will be coded using the most current version of Medical Dictionary for Regulatory Activities (MedDRA®) available at Celerion and summarized by treatment (2 active dose levels and pooled placebo) for the number of patients reporting the treatment emergent adverse event (TEAE) and the number of TEAEs reported. A by-patient AE data listing including verbatim term, coded term, treatment, severity, and relationship to study drug will be provided.

Safety data including ECGs, vital signs assessments, clinical laboratory results, and vascular access site reaction will be summarized by treatment (2 active dose levels and pooled placebo) and point of time of collection.

Descriptive statistics using appropriate summary statistics will be calculated for quantitative safety data as well as for the difference to baseline, when appropriate. In addition, a shift table describing out of normal range shifts will be provided for clinical laboratory results.

Concomitant medications will be listed by patient and treatment (2 active dose levels and pooled placebo) and coded using the most current version of the World Health Organization drug dictionary available at Celerion. Medical history will be listed by patient.

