7.4 Clinical Laboratory Tests (Serum Chemistry, Hematology, Coagulation and Urinalysis)

Safety serum chemistry, hematology and urinalysis tests are performed at Screening, Day -8 check-in, and end of HD on Day 3. For anuric patients, urinalysis may not be performed. Coagulation is collected at Screening, Day -8 check-in, start and end of

HD on Days -7, -5, -2, 1, and 3, and at Follow-up. Platelet count is collected at start and end of HD on Days -7, -5, -2, 1, and 3.

Out-of-range values and clinically significant results will be listed.

For serum chemistry and hematology laboratory values, descriptive statistics will be presented for each laboratory test by assessment time point and treatment. Change from baseline will be summarized in a similar manner. Baseline is defined as the result closest and prior to dose which may include unscheduled results. This will typically be the result collected at Day -8 check-in. Postdose unscheduled events or early termination results will not be included in summaries.

For each serum chemistry and hematology laboratory test, a shift table will be developed to compare the frequency of the results at baseline (above normal, normal, or below normal) with the respective postdose results.

For coagulation tests (aPTT, PT/INR, fibrinogen, and TT) and platelet count on HD days, summary will be for pre- and post-HD and fold change. Coagulation parameters and platelet count will be listed and presented together since they have the same timepoints. Urinalysis test results will be listed only.

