			Mean	X.XX	X.XX	X.XX	X.XX	X.XX	X.XX	X.XX	X.XX	X.XX
			SD	X.XXX	X.XXX	X.XXX	X.XXX	X.XXX	X.XXX	X.XXX	X.XXX	X.XXX
			Minimum	X.XX	X.XX	X.XX	X.XX	X.XX	X.XX	X.XX	X.XX	X.XX
			Median	X.X	X.X	X.X	X.X	X.X	X.X	X.X	X.X	X.X
			Maximum	XX.X	XX.X	XX.X	XX.X	XX.X	XX.X	XX.X	XX.X	XX.X

<include all remaining HD days>

Programmer note: This table will include aPTT, PT, INR, PT/INR, fibrinogen, TT from coagulation and platelet count from hematology. for PT, INR and PT/INR, the pre-dialysis value will be the baseline value for that day and the "change from baseline" will be the fold change from baseline "ie. Post-dialysis / Pre-dialysis.

Note: # = Lowest of the lower ranges and highest of the higher ranges are used. Refer to Appendix 16.1.10.1 for the breakdown.
 Fold change = Post-dialysis / Pre-dialysis

Program: /AAXXXX/ECR/sas_prg/stsas/tab_PROGRAMNAME.sas DDMMYYYY HH:MM

Table 14.3.5.6 Vital Sign Summary and Change from Baseline(Safety Population)

Vital Sign(unit)	Time Point	Statistic	Dose Level of E-WE Thrombin			Change from Baseline*		
			1.5 µg/kg	3.0 µg/kg	Placebo (Pooled)	1.5 µg/kg	3.0 µg/kg	Placebo (Pooled)
XXXXXXXXXX (unit)	Screen	n	XX	XX	XX			
		Mean	X.XX	X.XX	X.XX			
		SD	X.XXX	X.XXX	X.XXX			
		Minimum	X.XX	X.XX	X.XX			
		Median	X.X	X.X	X.X			
		Maximum	XX.X	XX.X	XX.X			
<Also include Days -8, -7, -5 and -2>								
Baseline*		n	XX	XX	XX			
		Mean	X.XX	X.XX	X.XX			
		SD	X.XXX	X.XXX	X.XXX			
		Minimum	X.XX	X.XX	X.XX			
		Median	X.X	X.X	X.X			
		Maximum	XX.X	XX.X	XX.X			
Day X, Hour X.XX		n	XX	XX	XX	XX	XX	XX
		Mean	X.XX	X.XX	X.XX	X.XX	X.XX	X.XX
		SD	X.XXX	X.XXX	X.XXX	X.XXX	X.XXX	X.XXX
		Minimum	X.XX	X.XX	X.XX	X.XX	X.XX	X.XX
		Median	X.X	X.X	X.X	X.X	X.X	X.X
		Maximum	XX.X	XX.X	XX.X	XX.X	XX.X	XX.X

Note: * Baseline is defined as the result closest and prior to the dose on Day 1.

Program: /AXXXXXX/ECR/sas_prg/stsas/tbl PROGRAMNAME.sas DDMMYYYY HH:MM

Table 14.3.5.7 Summarization of Weight (Safety Population)

Time Point	Statistic	Dose Level of E-WE Thrombin		
		1.5 µg/kg	3.0 µg/kg	Placebo (Pooled)
Screen	n	XX	XX	XX
	Mean	X.XX	X.XX	X.XX
	SD	X.XXX	X.XXX	X.XXX
	Minimum	X.XX	X.XX	X.XX
	Median	X.X	X.X	X.X
	Maximum	XX.X	XX.X	XX.X
Day -8, Check-in	n	XX	XX	XX
	Mean	X.XX	X.XX	X.XX
	SD	X.XXX	X.XXX	X.XXX
	Minimum	X.XX	X.XX	X.XX
	Median	X.X	X.X	X.X
	Maximum	XX.X	XX.X	XX.X
Day -7, Before HD	n	XX	XX	XX
	Mean	X.XX	X.XX	X.XX
	SD	X.XXX	X.XXX	X.XXX
	Minimum	X.XX	X.XX	X.XX
	Median	X.X	X.X	X.X
	Maximum	XX.X	XX.X	XX.X

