Appendix 16.2.8.1.1 Clinical Laboratory Report - Serum Chemistry (Safety Population)

Subject Cohort/ Number	Age#/ Treatment	Study Sex	Visit	Parameter1	Parameter2	Parameter3	Parameter4	Parameter5	Parameter6
				< Range> (Unit)	< Range> (Unit)	< Range> (Unit)	< Range> (Unit)	< Range> (Unit)	< Range> (Unit)
X	1/A	XX/X	Screen X	DDMMYYYY DDMMYYYY	XX H XX L +	XX XX L	XX XX L	XX H XX	XX XX

Programmer Note: Replace Parameter1, 2 etc. with actual lab tests in the study. Sort unscheduled assessment and early term chronologically with other scheduled assessments.

Programmer Note: Please adjust layout based on what is actually in the database if necessary.

Note: Treatment: A = 0.5 µg/kg bolus dose of E-WE Thrombin followed by a 0.25 µg/kg/hour continuous infusion over 4 hours for a total dose of 1.5 µg/kg

B = 1.0 µg/kg bolus dose of E-WE Thrombin followed by a 0.5 µg/kg/hour continuous infusion over 4 hours for a total dose of 3.0 µg/kg

P = Placebo

#Age is calculated from the date of first dosing. F = Female; M = Male

H = Above reference range, L = Below reference range

PI interpretation: + = Clinically Significant

Program: /AAXXXX/sas_prg/stsas/lis_PROGRAMNAME.sas DDMMYYYY HH:MM

Appendix 16.2.8.1.3 Clinical Laboratory Report - Coagulation and Platelet Count (Safety Population)

Subject Number	Cohort/ Treatment	Age#/ Sex	Study Visit	Study Hour	Date	Parameter1 < Range> (Unit)	Parameter2 < Range> (Unit)	Parameter3 < Range> (Unit)	Parameter4 < Range> (Unit)	Parameter5 < Range> (Unit)	Parameter6 < Range> (Unit)
X	1/A	XX/X	Screen X		DDMMYYYY XX XX	XX H XX L +	XX L	XX XX	XX XX L	XX H XX	XX XX

Programmer Note: A study hour column is included for coagulation and platelet count due to more frequent assessments. Replace Parameter1, 2 etc. with actual lab tests in the study. Sort unscheduled assessment and early term chronologically with other scheduled assessments.

Programmer Note: Please adjust layout based on what is actually in the database if necessary. Remove Other if no other tests. This listing includes PT/INR, fibrinogen, and TT from coagulation and platelet count from hematology.

Note: Treatment: A = 0.5 µg/kg bolus dose of E-WE Thrombin followed by a 0.25 µg/kg/hour continuous infusion over 4 hours for a total dose of 1.5 µg/kg

B = 1.0 µg/kg bolus dose of E-WE Thrombin followed by a 0.5 µg/kg/hour continuous infusion over 4 hours for a total dose of 3.0 µg/kg

P = Placebo

#Age is calculated from the date of first dosing. F = Female; M = Male

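### Day 14 coagulation has no summary by treatment and coagulation has no shift table, departures from protocol 14.3.1 that the SAP does not declare

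*SAP*

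**What the plan says.** Protocol 10.1.1 brings every dosed patient back on Day 14 (± 2 days) "for coagulation tests, immunogenicity sample collection, and to determine if any AE has occurred since the last study visit". SAP 7.4 gives the same coagulation schedule: Screening, Day -8, the start and end of "HD on Days -7, -5, -2, 1, and 3, and at Follow-up".

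On the summary, SAP 7.4 says: "For coagulation tests (aPTT, PT/INR, fibrinogen, and TT) and platelet count on HD days, summary will be for pre- and post-HD and fold change". The Table 14.3.5.5 shell in SAP 10.3 has rows for Screening, Day -8 and a generic HD day, followed by the instruction "<include all remaining HD days>". The shell shared by chemistry and hematology, by contrast, asks for every time point.

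On out-of-range results, protocol 14.3.1 states that "a shift table describing out of normal range shifts will be provided for clinical laboratory results". It also promises laboratory summaries by treatment and collection time. SAP 7.4 narrows the shift tables: "For each serum chemistry and hematology laboratory test, a shift table will be developed". SAP 9.2 accordingly lists shift tables only for those two groups (Tables 14.3.5.2 and 14.3.5.4). SAP Section 8 declares no departure from the protocol's analyses.

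The SAP does plan a by-patient display of out-of-range hematology and coagulation values (Table 14.3.4.2) and a full coagulation listing (Appendix 16.2.8.1.3).

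**The concern.** Coagulation tests are named in the primary outcome measures (protocol 9.2), to be judged against pre-treatment and placebo. Day 14 is the last safety contact. By SAP 7.4, chemistry, hematology and urinalysis end on Day 3, so coagulation is the only one of the routine laboratory groups drawn at follow-up.

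If the SAP is followed as written, the report will contain no Day 14 coagulation result by arm. It will have no comparison of Day 14 with the pre-dose value, and no count by arm of patients who moved in or out of the reference range on any coagulation test. A reader could recover these only by working through listings. Because Section 8 claims alignment, nothing would tell that reader that the protocol had promised more.

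**Working it through.** **1. Reproduce the plan's count.** The blood-volume table in protocol 13.8 gives 12 on-study coagulation time points at 3.5 mL each, 42 mL in total. From the flow chart and SAP 7.4:

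- Day -8 check-in: 1
- Five HD sessions (Days -7, -5, -2, 1, 3), start and end: 5 × 2 = 10
- Follow-up: 1
- Total: 1 + 10 + 1 = 12, and 12 × 3.5 = 42 mL. Both figures reproduce.

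**2. Count what the table covers.** The shell has Day -8 and all HD days: 1 + 10 = 11 of 12. The missing point is Follow-up.

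**3. Repeat for post-dose points.** Dosing is at the start of HD on Day 1, so the Day 1 pre-HD draw is pre-dose and four draws follow it:

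| Post-dose draw | Row in Table 14.3.5.5 | Compared with Day 1 pre-HD | In a shift table |
|---|---|---|---|
| Day 1 post-HD | yes | yes, by same-day fold change | no |
| Day 3 pre-HD | yes | no | no |
| Day 3 post-HD | yes | no, compared with Day 3 pre-HD | no |
| Follow-up | no | no | no |

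So 3 of 4 post-dose points are summarised by arm, 1 of 4 is compared with the pre-dose value, and 0 of 4 enters a shift table.

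**4. Check the title against the shell.** The table list in SAP 9.2 titles Table 14.3.5.5 as a summary with change from baseline. The shell's title omits the change, and its body defines fold change as post-dialysis over pre-dialysis on the same day. The listed title therefore promises more than the shell delivers.

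**5. Is coagulation a clinical laboratory result?** Protocol 13.2.7, on clinical laboratory tests, has a coagulation group (PT/INR, aPTT, fibrinogen, TT). The opening of protocol Section 13 includes coagulation among the clinical laboratory parameters. The heading of SAP 7.4 does the same. On that reading, the protocol's shift table should cover coagulation. The SAP covers 2 of the 3 blood laboratory groups, and none of the four coagulation tests.

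**6. Out-of-range displays that include coagulation.** There is one by-patient display (Table 14.3.4.2), with treatment, visit, high/low flags and clinical significance. There is no tabulation by arm.

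**The case against.** The strongest reply is that the data are not lost. An abnormal Day 14 value would appear in Table 14.3.4.2 with the patient's treatment and visit, and every value would appear in Appendix 16.2.8.1.3. This stands. A reader might infer that coagulation has no out-of-range display at all, and the documents contradict that. What is missing is counts and denominators by arm.

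A second reply is that nothing bars a Day 14 row. SAP Section 10 warns that shells may not cover every aspect of the study, and the Screening and Day -8 rows show that the table is not confined to HD days. This also stands as far as it goes: the gap is an omission, and the documents do not show a deliberate exclusion. But the text of 7.4 and the shell point the same way. A summary defined as pre-HD, post-HD and fold change has no place for a visit without HD, so the shell disclaimer does not supply the missing row.

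Third, the protocol's wording is not airtight. Protocol 9.2 names clinical laboratory tests and coagulation tests separately, and protocol 14.3 lets the SAP modify planned analyses. The passages in step 5 make the inclusive reading the better one. A permitted change should still be stated in SAP Section 8.

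Fourth, the practical yield may be small. In the first-in-human study, aPTT was back to baseline by 24 hours at every bolus dose, and Days 1 and 3 are already tabulated here. That limits the weight of the point but does not remove it: this trial uses a bolus plus infusion in a different population.

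Two further inferences should be resisted. One is that Day 14 coagulation serves as the functional check for antibodies that cross-react with thrombin. The documents do not say so; protocol 8.4 and 13.4.2 assign that risk to antibody assays. The other is that aPTT will be left out of the listing, because the programmer note reads "This listing includes PT/INR, fibrinogen, and TT from coagulation and platelet count from hematology". SAP 7.4 names aPTT among the coagulation tests and says they will be listed, SAP Section 7 lists all CRF data, and the same note says to insert the actual tests. This is a clerical slip.

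**Conclusion.** The point holds in this form. Day 14 coagulation, 1 of 12 on-study and 1 of 4 post-dose time points, has no summary by treatment. Coagulation has no shift table for any of its four tests, although protocol 14.3.1 is best read as promising one, and Section 8 does not declare the change. The planned listings mean that individual abnormal values will be visible, so this is a gap in the by-arm presentation of a primary safety measure and not a loss of data.

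The planned groups are 12, 12 and 12 (pooled placebo). The counts by visit assume that the schedule in SAP 7.4 is followed; how many of the 36 planned patients contribute at Day 14 depends on how many are dosed and return. The shift-table part rests on reading coagulation as a clinical laboratory result. The point should be corrected, though it does not threaten the study's main descriptive results.

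**What to change.** - Add a Follow-up row to Table 14.3.5.5, with change from the Day 1 pre-HD (pre-dose) value, and amend SAP 7.4 to match. Platelet count is not scheduled at follow-up, so the row applies to the coagulation tests only.
- Add a coagulation shift table by treatment, from Day 1 pre-HD to each post-dose point: Day 1 post-HD, Day 3 pre-HD, Day 3 post-HD and Follow-up.
- If the sponsor prefers not to add either, declare and justify the departure in SAP Section 8.
- As a clerical correction, add aPTT to the programmer note for Appendix 16.2.8.1.3.

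The cost is one row, one table and a sentence in 7.4. No new samples or data are needed, and the reference ranges are already required for the out-of-range flags.

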11. LISTING SHELLS

The following listing shells provide a framework for the display of data from this study. The shells may change due to unforeseen circumstances. These shells may not be reflective of every aspect of this study, but are intended to show the general layout of the listings that will be presented and included in the final CSR. These listings will be generated off of the Celerion SDTM datasets (SDTM Tabulation Model 1.4 mapped in accordance with SDTM Implementation Guide 3.2). All listings will be presented in Courier New font size 9.

Appendix 16.1.10.1 Clinical Laboratory Reference Ranges

Laboratory Group	Test Name	Sex	Age Category	Reference Range	Unit
Serum Chemistry	Test Name	XXXXXX	XX	XX - XX	units
	Test Name	XXXXXX	XX	XX - XX	units
	Test Name	XXXXXX	XX	XX - XX	units
	Test Name	XXXXXX	XX	XX - XX	units
	Test Name	XXXXXX	XX	XX - XX	units
	Test Name	XXXXXX	XX	XX - XX	units
Hematology	Test Name	XXXXXX	XX	XX - XX	units
	Test Name	XXXXXX	XX	XX - XX	units
	Test Name	XXXXXX	XX	XX - XX	units
	Test Name	XXXXXX	XX	XX - XX	units
	Test Name	XXXXXX	XX	XX - XX	units

<similar for remaining Laboratory Groups and Test Names>

Programmer note: Please add a column for site ID if multiple sites are used.

Program: /CAXXXX/sas_prg/stsas/lis_PROGRAMNAME.sas DDMMMYYYY HH:MM

Appendix 16.2.1 Study Completion/Early Termination (Safety Population)

Subject Number	Cohort/ Treatment	Completed Study?	Date	Date of Last Contact	Reason for Discontinuation	Comments
X	1/A	Yes	DDMMYYYY	DDMMYYYY		
X	1/A	Yes	DDMMYYYY	DDMMYYYY		
X	1/P	Yes	DDMMYYYY	DDMMYYYY		
X	1/A	Yes	DDMMYYYY	DDMMYYYY		
X	1/A	No	DDMMYYYY	DDMMYYYY	XXXXXXXXXXXX	XXXXXXX
X	1/P	Yes	DDMMYYYY	DDMMYYYY		

Note: Treatment: A = 0.5 µg/kg bolus dose of E-WE Thrombin followed by a 0.25 µg/kg/hour continuous infusion over 4 hours for a total dose of 1.5 µg/kg
B = 1.0 µg/kg bolus dose of E-WE Thrombin followed by a 0.5 µg/kg/hour continuous infusion over 4 hours for a total dose of 3.0 µg/kg
P = Placebo

Program: /AXXXXX/sas_prg/stsas/lis_PROGRAMNAME.sas DDMMYYYY HH:MM

Appendix 16.2.4.1 Demographics (Safety Population)

Subject Number	Cohort/ Treatment	Date of Birth	Age* (yrs)	Gender	Race	Ethnicity	Height (cm)	Weight (kg)	Body Mass Index (kg/m ²)	Informed Consent Date
X	1/A	MMYYYY	XX	AAAAAA	AAAAAAA	AAAAAAAAA	XXX	XX.XX	XX.XX	DDMMYYYY
X	1/A	MMYYYY	XX	AAAAAA	AAAAAAA	AAAAAAAAA	XXX	XX.XX	XX.XX	DDMMYYYY
X	1/P	MMYYYY	XX	AAAAAA	AAAAAAA	AAAAAAAAA	XXX	XX.XX	XX.XX	DDMMYYYY

Note: *Age is calculated from the date of informed consent.

Treatment: A = 0.5 µg/kg bolus dose of E-WE Thrombin followed by a 0.25 µg/kg/hour continuous infusion over 4 hours for a total dose of 1.5 µg/kg
B = 1.0 µg/kg bolus dose of E-WE Thrombin followed by a 0.5 µg/kg/hour continuous infusion over 4 hours for a total dose of 3.0 µg/kg
P = Placebo

Program: /AXXXXX/sas_prg/stsas/lis_PROGRAMNAME.sas DDMYYYY HH:MM

Appendix 16.2.4.2 Physical Examination (Safety Population)

Subject Number	Cohort/ Treatment	Study Visit	Study Time	Date	Body System	Result	Abnormality	Clinical Significance
X	1/A	Screen		DDMMYYYY	1. General Appearance	Abnormal	XXXXXXXXXXXXXXXXXXXX	NCS

Note: Treatment: A = 0.5 µg/kg bolus dose of E-WE Thrombin followed by a 0.25 µg/kg/hour continuous infusion over 4 hours for a total dose of 1.5 µg/kg

B = 1.0 µg/kg bolus dose of E-WE Thrombin followed by a 0.5 µg/kg/hour continuous infusion over 4 hours for a total dose of 3.0 µg/kg

P = Placebo

Program: /AXXXXX/sas_prg/stsas/lis_PROGRAMNAME.sas DDMMYYYY HH:MM

Appendix 16.2.4.3 Medical and Surgical Histories (Safety Population)

Subject Number	Cohort/ Treatment	Seq #	Description	Date of Diagnosis/Surgery		
				Start	End	Ongoing?
X	1/A	X	XXXXXX XXXXX XXXXXXXX	MMYYYY		Yes
		X	XXXXXXXXXX	MMYYYY	MMYYYY	No
		X	XXXXXXXX XXXXX XXXXXX	MMYYYY	MMYYYY	No

Note: Treatment: A = 0.5 µg/kg bolus dose of E-WE Thrombin followed by a 0.25 µg/kg/hour continuous infusion over 4 hours for a total dose of 1.5 µg/kg
B = 1.0 µg/kg bolus dose of E-WE Thrombin followed by a 0.5 µg/kg/hour continuous infusion over 4 hours for a total dose of 3.0 µg/kg
P = Placebo

Program: /AXXXXXX/sas_prg/stsas/lis_PROGRAMNAME.sas DDMMMYYYY HH:MM

Appendix 16.2.4.4 Alcohol Screen (Safety Population)

Subject Number	Cohort/ Treatment	Study Visit	Visit Date	Type of Sample	Actual Time	Result
X	1/A	Screen	DDMMYYYY	Breath	HH:MM	Negative

Note: Treatment: A = 0.5 µg/kg bolus dose of E-WE Thrombin followed by a 0.25 µg/kg/hour continuous infusion over 4 hours for a total dose of 1.5 µg/kg

B = 1.0 µg/kg bolus dose of E-WE Thrombin followed by a 0.5 µg/kg/hour continuous infusion over 4 hours for a total dose of 3.0 µg/kg

P = Placebo

Program: /AAXXXX/sas_prg/stsas/lis_PROGRAMNAME.sas DDMMYYYY HH:MM

Appendix 16.2.4.5 Saliva Drug Screen (Safety Population)

Subject Number	Cohort/ Treatment	Study Visit	Visit Date	Actual Time	Result	If Positive, list all that were positive:
X	1/A	Screen	DDMMYYYY	HH:MM	Negative	

Note: Treatment: A = 0.5 µg/kg bolus dose of E-WE Thrombin followed by a 0.25 µg/kg/hour continuous infusion over 4 hours for a total dose of 1.5 µg/kg

B = 1.0 µg/kg bolus dose of E-WE Thrombin followed by a 0.5 µg/kg/hour continuous infusion over 4 hours for a total dose of 3.0 µg/kg

P = Placebo

Program: /AAXXXX/sas_prg/stsas/lis_PROGRAMNAME.sas DDMMYYYY HH:MM

Aronora, Inc.
E-WE thrombin, Protocol EWE-19-02
Celerion, Clinical Study Report No. CA26622

